3.3. Data Analysis and Data Monitoring

3.3.1 *Strategies to Minimize Missing Data.*

At the time of enrollment, we will gather the preferred and all available email addresses, phone numbers (including mobile for text messaging), and social networking inbox addresses for eligible adolescents. To confirm accuracy of the email address, participant payments will be sent electronically, via email, and participants will be instructed to contact study staff if payment is not received. We will also collect phone numbers for 3 friends or family members who would know how to reach the participant if we do not. Our experience is that we can maintain >85% of our enrollees over the course of the study. Despite our best efforts, we expect some attrition over the course of follow up, which has been factored into our sample size calculations. In the case that an adolescent does not have an email address, surveys will be completed by phone and payments will be sent via mail.

Maintaining statistical power is a key consideration. We will implement various recommended strategies for maximizing power within the current design, including use of covariates in data analyses when appropriate, preventing attrition and missing data, implementing advanced missing data analyses such as multiple imputation techniques using reliable measures, and maintaining integrity of the intervention throughout the study. For all analyses, we will start with models using all available data, not just complete cases. In addition we will apply inverse probability weighted methods to adjust for missing data and conduct sensitivity analyses looking at how other estimates are impacted by including the variables with missing values.

3.3.2 *Data Analysis.*

Data from the web-based surveys will be uploaded into STATA analytic software. Prior to analysis, all variables will be checked for validity, missingness, and distributional assumptions. Preliminary analyses required for variable construction, any required imputation of missing data, assessment of psychometric properties of scale scores, and assessment of the validity of study variables will be completed before analyses assessing

intervention effects. Data set documentation will then be developed and distributed to the study team. Before carrying out analyses addressing each of the research questions, an analysis plan will be formally presented to the study team and Project Advisory Board so a wide range of expertise and experience is brought to bear on each work product of the team.

Some key features of the stepped wedge design require special consideration in the planned analyses. First, the design involves unidirectional cross-over from the control arm to the intervention arm for all PCPs. This has to be captured by an indicator specific to PCP and time point. Second, there are natural hierarchical structures in the data with PCPs nested within clinics, patients nested within PCPs, and repeated assessments made within patients for some outcomes, such as health risk behaviors. Because different patient samples will be surveyed at each time point, within patient correlation over time should not be strong. Still, clustering at the clinic and PCP-levels needs to be examined in all analyses. Third, secular time trends need to be carefully examined and separated from the intervention effect. Based on these considerations, we will focus on model-based approaches (linear or generalized linear mixed effects models) for the main analyses, in addition to standard hypothesis testing techniques.

Aim 1 will compare intermediary targets at all clinics before and after the intervention using an analytic approach that both accounts for design features, repeated assessments within adolescents, time trends in these target behaviors during study period and adjust for potential confounders. For this aim we will use patients as the units of analysis. We will consider outcomes at the level of the patient (adolescent reported motivation for health and provision of appropriate preventive counseling).

Our primary analysis will be based on a set of mixed effects regression models. As an illustration, let's consider the adolescent self-reported health motivation (readiness to change, as other adolescent reported outcomes can be modelled in a similar fashion. Specifically, we will consider the following regression model:

$$Y_{ijk} = \mu + \alpha X_{ijk} + \beta_k T_k + \gamma_k X_{ijk} * T_k + b_i + b_{ij} + \varphi \text{Covariates} + \varepsilon_{ijk},$$

in which Y_{ijk} denotes the health motivation reported by j th patient within i th provider at k th time interval, X_{ijk} is a binary indicator of exposure to the intervention for the provider and the predictor of interest, T_k is a binary indicator of the k th assessment, b_i and b_{ij} are PCP and adolescent specific random effects that account for the within PCP and within adolescent correlations, and ε_{ijk} is the error term. Additional patient-level or PCP-level confounding variables can be adjusted in the model as well.

With this model, the fixed effects α captures the treatment effects on mean responses and time-by-intervention interaction coefficients γ_k 's captures the treatment effects across time. Fixed effects β_k 's aim to capture any temporal trend or learning effects. Using this approach, both within-adolescents and between adolescents information will be used to estimate the treatment effects. All coefficients will be tested using Wald test. Also note this

model framework is flexible enough that a patient can be enrolled at any time during the study and the model can accommodate different numbers of post-intervention assessments. For example, for an adolescent enrolled after his/her PCP has received intervention, all X_{ijk} 's would take value 1 for that subject.

We will apply linear mixed effects models for Gaussian outcome Y_{ijk} , and generalized linear mixed effects models for other types of outcomes (e.g., logistic model for binary outcome).

For *Aim 2*, analyses will be based on patient survey responses to the 8-item satisfaction scale, patient perception of PCP communication, and the summary health risk variable, which will all be treated as continuous response variables. The summary health risk variable constructed from a count of dichotomized key risk behaviors (as shown in Table 2). First, satisfaction levels and risk behaviors will be summarized for each period (pre- and post-intervention) and will be compared using two sample t-tests. For the main analysis, we will apply mixed effects models similar to those proposed in Aim 1 to examine the intervention effect. For patient satisfaction, PCP satisfaction, adolescent's perception of PCP communication and health risk behaviors, the analysis will be cross-sectional comparisons at one day following the primary care visit. Let Y_{ij} denotes the satisfaction at one-day post visit of adolescent j within PCP i , let X_{ij} denote whether the PCP has received intervention at the time of visit, then the following mixed effects model can be applied

$$Y_{ij} = \mu + \alpha X_{ij} + b_i + \varphi \text{Covariates} + \varepsilon_{ij},$$

where b_i accounts for within-PCP correlations for adolescents seen by the same PCP. The fixed effect α captures the intervention effect on the patient satisfaction. Similar model can be applied to PCP outcomes and we can account for within-clinic correlations as well.

When examining the intervention effects on adolescents individual risky behaviors (alcohol use, marijuana use, unprotected sexual activity, depression, physical activity, healthy food consumption, seatbelt and helmet use) at baseline, 3, 6, and 12 months after the primary care visit, same modeling framework as outlined for Aim 1 can be applied.

3.3.3 Heterogeneity of Treatment Effects.

The goal of any heterogeneity of treatment effects analyses will be to ascertain whether treatment effects vary significantly across subgroups of patients and to identify subgroups of patients that achieve the greatest benefit from part or entire treatment regimen. (PCORI Methodology Standard HT-1) Based on our current knowledge, we hypothesize that treatment effects may vary substantially across age groups (13-15 yrs vs. 16-19 yrs), gender groups (male vs. female), racial groups (White, African American, Asian/American Indian/Pacific Islander, and multi-racial), ethnic groups (Hispanic vs. non-Hispanic), adolescents with differential baseline motivation status (highly motivated adolescents vs. less motivated), and adolescents with differential self-efficacy (high vs. low) (PCORI Methodology Standard HT-2). We recognize the possibility that additional subgroups may

arise in the course of the analyses described above as we identify which factors modify the associations. (PCORI Methodology Standard HT-4) Our stepped wedge design allows us to employ both within participants and between participants information to estimate and compare treatment effects.

As we have outlined in the Statistical Analysis section, the primary analysis will be based on mixed-effects regression models in the following form, for example, when examining PCP outcomes (similar models will be applied to adolescent outcomes):

$$Y_{ijk} = \mu + \alpha X_{ijk} + \beta_k T_k + b_i + b_{ij} + \gamma \text{covariates} + \epsilon_{ijk},$$

in which Y_{ijk} denotes the appropriate preventive counseling rate for j th PCP within i th clinic at time interval k , X_{ijk} is a binary indicator of exposure to the intervention (predictor of interest), T_k is a binary indicator of the k th assessment time interval, b_i and b_{ij} are clinic and PCP specific random effects that account for the within clinic and within PCP correlations, ϵ_{ijk} is the error term. Adjustment for additional clinic-level or PCP-level confounding variables can be incorporated into the model as well. With this model, the fixed effect α captures the treatment effect, while fixed effects β_k 's aim to capture any temporal trend. Using this approach, both within-PCP and between PCP information will be used to estimate the treatment effect.

Our treatment heterogeneity (TH) analysis will consist of two steps. The first step will be subgroup analysis, in which the above outlined regression models will be applied to each of the subgroups. We will then inspect the treatment effect sizes and significances across subgroup analyses to get a sense of the direction and magnitude of treatment heterogeneity. In second step we will formally test the treatment heterogeneity by including a treatment-by-group interaction term in the model:

$$Y_{ijk} = \mu + \alpha_1 X_{ijk} + \alpha_2 \text{Group} + \alpha_3 X_{ijk} * \text{Group} + \beta_k T_k + b_i + b_{ij} + \gamma \text{covariates} + \epsilon_{ijk},$$

A wald t-test on the coefficient α_3 formally tests the significance of treatment heterogeneity across groups. (PCORI Methodology Standard HT-3) We may have to apply multiple comparisons adjustments to minimize false discovery rates due to large number of subgroup analyses.

Treatment heterogeneity can also be interpreted as effect modification, i.e., the treatment effects are being modified by group characteristics. However, such modifications may work through different mechanisms. For example, same intervention may be received differentially by different groups with one group embrace every aspect of the intervention and the other group does not comply at all. Or, different groups may respond differentially to the different treatment components, with one group respond better to one part of the intervention and another group to another part of intervention. Therefore, when examining treatment heterogeneity, we will have to apply careful scientific reasoning and scrutinizing, in addition to statistical analysis.

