During the intervention period, participating PCPs will receive adolescent-centered communication training, based on the tenets of motivational interviewing, to reinforce healthy behavior choices and to engage youth and parents to reduce risk behaviors as appropriate. PCPs will also receive three feedback reports (baseline, 2 months and 4 months) on adolescent-reported receipt of counseling on each of the target behaviors and adolescent-reported visit satisfaction and follow-up care. PCPs will not be asked to complete any study questionnaires; all of the outcome data will be gathered directly from adolescents and caregivers. Outcome data for the three feedback reports will be given to providers in aggregate form and will be void of individual identifiers.

Adolescents in the intervention group will receive full personalized motivational feedback following completion of the screening survey, both with web-based delivery. Their PCPs will receive a summary report which will include specific information on the adolescent's responses that will allow them to reinforce healthy behavior choices and implement further brief, in-person interventions for moderate to high risk adolescents. The personalized feedback to the participant and provider is consistent with current standard of care. However, the electronic method of delivery is unique to this project.

In order to administer follow-up surveys, we will ask adolescents to provide an email address, cell phone number, or phone number. One day (T2) following their PCP appointment, adolescent participants will be asked via email, text message or phone to complete a survey about their motivation for health, perception of PCP communication, and experiences. Both adolescents and their caregivers will be asked about their satisfaction with treatment during the appointment with their PCP. In addition, caregivers will be asked open-ended questions to assess the provider's delivery of caregiver education regarding strategies to reduce health risks for their child during the visit.

Three (T3), six (T4) and twelve (T5) months following their PCP appointment, adolescent participants will be asked via email, text message or phone to complete all assessments

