3.2. Measures by Construct and Time point

Tables 1 and 2 describe the study measures by construct.

Table 1: Measures used in the study, organized by construct and method.

Measures and Constructs	Time point
Moderators	
Gender, age, race, household composition, school, truancy, support, goals, interest in discussing health risks with provider	T1(A)
Number of visits with provider	T2(A)
Health Self-Efficacy	T1(A), T2 (A), T3(A), T4(A), T5(A)
Caregiver Concerns	
Guidelines for Adolescent Preventative Services Caregiver Questionnaire: adolescent health risk behavior concerns.	T1(C)
Perception of provider engagement with the caregiver	T2 (C)
Intermediary Targets	
Health Motivation (Readiness to Change Rulers): Self-report used to assess adolescent motivation for change among specific health behaviors.	T1(A), T2 (A), T3(A), T4(A), T5(A)
Adolescent Report of the Visit: adolescent-report of the PCPs' delivery of risk behavior screening and counseling based on risk level.	T2 (A)
Interval Receipt of Care: adolescent self-report of extent of follow up care.	T3 (A), T4(A), T5(A)
Main Outcomes: Satisfaction & Perception of PCP Communication	

Satisfaction Questionnaire: self-report of satisfaction with care based on items adapted from the Consumer Assessment of Healthcare Providers and Systems (CAHPS) measure.	T2(A/C)
Adolescent Perception of Patient-Centeredness: adolescent self-report of how adolescents feel about visits with their primary caregiver.	T2(A)
Main Outcomes: Health Risk Dimensions*	
Alcohol Consumption and Marijuana Use: self-report based on items about typical quantity and frequency of drinking, smoking/using tobacco, and marijuana use (each calculated separately) over the past 30 days.	T1(A), T3(A), T4(A), T5(A)
Fruit and Vegetable Screener: self-report of fruit and vegetable consumption.	T1(A), T3(A), T4(A), T5(A)
Physical Activity Screener: self-report of physical activity.	T1(A), T3 (A), T4(A),T5(A)
Sexual Risk: self-report of sexual activity, birth control, and condom use.	T1(A), T3(A), T4(A), T5(A)
Patient Health Questionnaire-9 (PHQ-9): self-report of DSM-V symptoms for depression.	T1(A), T3(A), T4(A), T5(A)
Safety: self-report to assess behaviors that contribute to unintentional injuries (e.g., seat belt use, helmet use).	T1(A), T3(A), T4(A), T5(A)

Key: T1 = Timepoint 1 (Baseline) T4 = Timepoint 4 (6 month)
T2 = Timepoint 2 (1-day) T5 = Timepoint 5 (1 year)
T3 = Timepoint 3 (3-month)
A = Adolescent survey

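### The rationale for weak within-adolescent correlation contradicts the survey schedule, and the single adolescent intercept can miscalibrate the wave-specific tests if correlation fades with time

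*Combined protocol and SAP*

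**What the plan says.** Section 3.3.2 lists features of the stepped wedge design that the analysis must respect. It acknowledges "repeated assessments made within patients for some outcomes, such as health risk behaviors", and in the next sentence sets the matter aside: "Because different patient samples will be surveyed at each time point, within patient correlation over time should not be strong". It then asks for clustering to be examined at clinic and PCP level.

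The schedule describes a cohort. Section 3.1: "Three (T3), six (T4) and twelve (T5) months following their PCP appointment, adolescent participants will be asked via email, text message or phone". Table 1 in section 3.2 places health motivation at T1 to T5 and each health risk measure at T1, T3, T4 and T5. Section 6.8 pays $20 per adolescent survey up to $100, which is five surveys.

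The Aim 1 model in section 3.3.2 has an exposure effect α, wave effects, wave-by-exposure effects γ_k, and random terms that "are PCP and adolescent specific random effects that account for the within PCP and within adolescent correlations". All coefficients are to be Wald-tested. Aim 2 reuses this framework for the individual risk behaviours. No serial correlation, random slope, unstructured covariance or robust standard error is named, and no sensitivity analysis on the covariance is planned.

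**The concern.** The stated reason is not true of the T1 to T5 assessments. Repeated answers by one adolescent to the same items will be correlated, and surveys weeks apart may well agree more closely than surveys a year apart.

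A random intercept gives every pair of waves the same correlation. The standard error of a change from T1 depends on the correlation between T1 and that particular wave. If an average correlation is used where the true one is lower, the contrast looks too precise; where the true one is higher, it looks too imprecise. The γ_k are planned tests of how the effect develops, so both false positives at 12 months and lost power at the early waves are possible.

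**Working it through.** **What can be reproduced.** The plan gives no within-adolescent correlation, alpha, power or effect size, so it has no figure of its own to check here. The survey count agrees: $100 / $20 = 5.

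**Inputs.** From the documents: waves T1, T2 (one day after the visit), T3, T4, T5 (3, 6 and 12 months after it); about 300 adolescents; more than 85% retained. Assumed: two-sided alpha 0.05; constant variance; T1 as reference wave; T1 about three weeks (0.75 months) before the visit; exposure X fixed per adolescent unless stated; and the decay patterns below, with m the gap in months.

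**Formula.** With near-complete data the random-intercept fit settles on the average variance v and average covariance c. Write S for the true covariance matrix. Then

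- for γ_k: model SE / true SE = sqrt[(2v − 2c) / (S_11 + S_kk − 2 S_1k)], which with constant variance is sqrt[(1 − mean ρ) / (1 − ρ_1k)];
- for the group difference at wave k, α + γ_k: sqrt(v / S_kk), which is 1 with constant variance;
- type I error = 2Φ(−1.96 × ratio).

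**Middle case, four waves, ρ = 0.8·exp(−m/20).**

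- T1 with T3, T4, T5 (gaps 3.75, 6.75, 12.75): 0.663, 0.571, 0.423.
- T3–T4, T3–T5, T4–T5 (gaps 3, 9, 6): 0.689, 0.510, 0.593.
- Mean = 3.449 / 6 = 0.575, so 1 − mean = 0.425.
- T3: sqrt(0.425 / 0.337) = 1.12, type I error 2.8%.
- T4: sqrt(0.425 / 0.429) = 1.00, 5.1%.
- T5: sqrt(0.425 / 0.577) = 0.86, about 9%.

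**Range.** Each cell gives the SE ratio and the type I error for γ_k.

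| Assumed ρ | T3, four waves | T5, four waves | T2, five waves | T5, five waves |
|---|---|---|---|---|
| 0.7·exp(−m/40) | 1.06, 3.8% | 0.91, 7.4% | 1.13, 2.7% | 0.90, 7.7% |
| 0.8·exp(−m/20) | 1.12, 2.8% | 0.86, 9% | 1.33, 0.9% | 0.84, 10.0% |
| 0.8·exp(−m/12) | 1.13, 2.6% | 0.86, 9.3% | 1.42, 0.5% | 0.83, 10.2% |

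**Stronger decay.** Take ρ = 0.5^(m/12), with gaps of 3, 6 and 12 months from T1. Correlations with T1 are 0.841, 0.707 and 0.500, and the mean over pairs is 0.698. T5: sqrt(0.302 / 0.500) = 0.78, type I error 12.8%. T3: sqrt(0.302 / 0.159) = 1.38, 0.7%.

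**Simulation check.** 300 adolescents, 15% lost by 12 months, 3,000 runs per pattern. For γ at T5 the rejection rate was 13.3% under 0.5^(m/12), 7.9% under a milder decay (closed form 8.2%), and 4.8% under exchangeable correlation.

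**Where the error vanishes or moves.**

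- Exchangeable correlation: every ratio is 1, so there is no error.
- Group difference at T5 with X fixed and constant variance: ratio 1. Simulated rejection under decay was 4.5 to 6.4%.
- X switching within an adolescent (steps of 3 to 4 months assumed, as the timeline figure is not shown): the T5 group difference has a type I error of 7 to 12%.
- Random slopes with X fixed (slope variance 0.10 to 0.50 of baseline variance at 12 months): 5.7 to 8.2% at T5, for γ and for the group difference.

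**The case against.** The strongest reply is that the sentence does no harm. It sits in a paragraph about the stepped wedge, where time points may mean successive recruitment periods, and different adolescents are indeed recruited in each. The model then includes the adolescent effect, which estimates the correlation whatever its size. Most of this stands. But on the recruitment reading the sentence says nothing about the T1 to T5 correlation, and the schedule contradicts any wider reading. An intercept estimates the size of the correlation, not its shape over time.

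A reader might infer three stronger things, none of which the documents support.

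- That adolescent clustering will be ignored. It will not: the Aim 1 model has the term, and Aim 2 reuses that framework for individual risk behaviours.
- That section 3.3.3 drops the adolescent effect, because its random terms "are clinic and PCP specific random effects that account for the within clinic and within PCP correlations". That equation is introduced as an example for PCP outcomes, with the PCP as the unit, so no adolescent term belongs there. The text simply does not write out the adolescent version.
- That the standard errors are wrong as a matter of fact, and worst at 12 months. The error depends on decay, which the documents neither assert nor exclude. Only the false-positive direction is worst at T5; the distortion at T2 can be larger, but it is conservative. Aim 2's comparison of rates with usual care at 12 months keeps its 5% level if X is fixed and variance is constant.

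It is also fair that the equation is offered as an illustration and that an analysis plan is to be presented before analysis. Nothing says that plan will settle the covariance.

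**Conclusion.** The concern holds in a limited form. The rationale in section 3.3.2 is inconsistent with the follow-up schedule and should be corrected. The planned model handles within-adolescent correlation, but under an equal-correlation assumption that is untested over gaps from weeks to a year.

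If correlation decays, the T1-to-T5 interaction test for a continuous outcome runs at about 7 to 10% instead of 5% (up to 13% under stronger decay), and the T2 and T3 tests lose power. These sizes rest on assumed correlations. They do not carry over to the logistic models for binary outcomes, which were not computed. Whether the 12-month group difference is touched depends on variance over time and on whether X can change within an adolescent. Section 3.3.2 hints that it can, since it defines the indicator by PCP and time point and draws on within-adolescent information, but it never says so outright.

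This should be fixed before analysis; it does not undermine the design.

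**What to change.** - Replace the sentence in section 3.3.2 with a statement that each adolescent is surveyed up to five times and that within-adolescent correlation is expected and modelled.
- For continuous repeated outcomes, pre-specify an unstructured within-adolescent covariance over the scheduled waves, alongside PCP and clinic effects. It takes the place of the adolescent intercept and contains the exchangeable case: 4 × 5 / 2 = 10 parameters for four waves and 5 × 6 / 2 = 15 for five, which about 300 adolescents can support. Name a fallback structure in case of non-convergence.
- State whether X switches during follow-up for an adolescent whose PCP crosses over.
- State that the adolescent-outcome versions of the section 3.3.3 models keep the within-adolescent term.
- For binary outcomes keep the adolescent random effect. If robust inference is added, use a permutation test or a small-cluster correction. An uncorrected sandwich would do more harm than good: in a simplified linear stepped wedge check (300 adolescents, assumed intraclass correlation 0 to 0.05) it gave a type I error of 19 to 22% clustering on 6 clinics and 8 to 19% on 30 PCPs.

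The cost is SAP wording, a different model option in Stata, a few more covariance parameters and possibly some convergence work. No data collection changes.

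### The longitudinal model never says how exposure is coded at 3, 6 and 12 months for adolescents seen before their PCP crossed over, and neither possible coding is safe in the model as written

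*Combined protocol and SAP*

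**What the plan says.** Section 3.3.2 first sets a requirement for the one-way crossover: "This has to be captured by an indicator specific to PCP and time point". The Aim 1 longitudinal model then defines exposure: "X_{ijk} is a binary indicator of exposure to the intervention for the provider and the predictor of interest". Its only worked case is that "for an adolescent enrolled after his/her PCP has received intervention, all X_{ijk} 's would take value 1 for that subject". No rule is given for an adolescent enrolled before crossover. The section adds that the number of post-intervention assessments may differ between patients, and that "both within-adolescents and between adolescents information will be used to estimate the treatment effects".

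On the other terms, alpha "captures the treatment effects on mean responses", gamma_k carries the effect across time, and "T_k is a binary indicator of the k th assessment". The section also says that "secular time trends need to be carefully examined and separated from the intervention effect".

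The model is an illustration for health motivation, "as other adolescent reported outcomes can be modelled in a similar fashion", and the Aim 2 text allows the same framework for individual risk behaviours.

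Group membership is defined differently elsewhere. Section 3.1 assigns it by whether the clinic appointment falls before or after implementation. The one-day model in Section 3.3.2 uses the PCP's status when the visit takes place. Section 4.4 provides a printed baseline report to the PCP only for post-implementation enrollees.

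**The concern.** Every PCP eventually crosses over, and adolescents are followed for 12 months. Many adolescents seen under usual care will therefore complete surveys after their PCP has been trained. They received no personalised feedback, and their PCP received no report on them. If X tracks the provider at the survey date, these surveys count as treated.

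Fixing X at the index visit avoids that but exposes a second gap. In a stepped wedge design intervention adolescents enrol later on average than controls. If T_k numbers assessments since the visit, nothing in the equation separates calendar time from exposure.

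At stake are the primary model for motivation, the framework for individual risk behaviours and, if modelled alike, follow-up care. Follow-up care is an Aim 1 target that Table 1 measures only at T3–T5, so it has no baseline from which to take a change. Counselling, satisfaction and patient-centredness are measured at one day and are not affected.

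**Working it through.** The documents state no effect size, ICC or error rate for this model, so there is no figure to reproduce.

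**Inputs from the documents.** Six clinics crossing one after another; about 5 PCPs per clinic; about 300 adolescents; surveys at baseline and at 3, 6 and 12 months.

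**Assumptions.** One clinic crosses every s = 2, 3, 4 or 6 months; 7 equal periods with even enrolment (6 × 7 × 7 = 294 adolescents); total variance 1, PCP ICC 0.05, within-adolescent correlation 0.1 to 0.5; true effect 1.0 at every follow-up and 0 at baseline; no spill-over to controls unless stated.

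**Step 1: control surveys coded X = 1 under survey-date coding.** At lag L months the share is Σ min(c·s, L) / Σ c·s, over c = 1 to 6. For s = 3 and L = 12: (3+6+9+12+12+12)/63 = 54/63 = 86%.

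| Step | 3 mo | 6 mo | 12 mo | Mean |
|---|---|---|---|---|
| 2 mo | 40% | 71% | 100% | 71% |
| 3 mo | 29% | 52% | 86% | 56% |
| 4 mo | 21% | 40% | 71% | 44% |
| 6 mo | 14% | 29% | 52% | 32% |

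If the last clinic crosses within 12 months of first enrolment (6s ≤ 12), every 12-month survey has X = 1. At s = 2 the eight fixed effects have rank 7, and the 12-month contrast cannot be estimated.

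**Step 2: what the coefficients estimate.** Let D hold the T_k and X·T_k columns (plus period terms where stated), V the covariance and m the expected outcomes. The model then estimates (D′V⁻¹D)⁻¹D′V⁻¹m. T1 is the reference; the truth is alpha = 0 and gamma_k = alpha+gamma_k = 1.0. Ranges run over step lengths (and over correlations 0.1 to 0.5 unless one is given); 12-month figures cover only estimable cases.

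*Survey-date X, no calendar trend*
- Alpha: −0.71 to −0.11.
- Alpha+gamma_k: 0.22–0.78 at 3 and 6 months, 0.27–0.61 at 12.
- Gamma_k at correlation 0.5: 0.92–0.99 at 3 and 6 months, 0.93–0.94 at 12. At correlation 0.1: 0.65–0.89 and 0.62–0.72.
- Follow-up care (T3–T5 only), 3 and 6 months: 0.43–0.78 at correlation 0.1, 0.23–0.51 at 0.5.

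*Survey-date X, assumed trend +0.5 per year*
- Correlation 0.1: alpha +0.01 to +0.62; alpha+gamma_k 0.68–1.52 at 3 and 6 months, above 1 at 4- and 6-month steps.
- Correlation 0.5: alpha+gamma_k 0.31–0.89.

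*X fixed at the index visit, same trend, no calendar terms*
- Alpha 0.25–0.79; alpha+gamma_k 1.25–1.79; gamma_k 1.00.
- Hand check: within a PCP the two groups' mean enrolment dates differ by 7s/2 = 3.5s months. Pooled over PCPs, the control mean is (s/2)(91/21) = 2.17s and the intervention mean 7s − 2.17s = 4.83s, a gap of 2.67s. At 0.5/12 per month, alpha should lie between 0.22 and 0.29 for s = 2 and between 0.67 and 0.88 for s = 6. It does.

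*X fixed plus enrolment-period terms, same trend*
- Alpha 0, alpha+gamma_k 1.00, follow-up care 1.00.

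*Survey-date X plus enrolment-period terms*
- Alpha −0.86 to −0.39; alpha+gamma_k 0.04–0.53 at 3 and 6 months. Calendar terms alone do not repair the coding.

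**Step 3: spill-over.** Suppose controls gain 50% of the effect once their PCP is trained. For follow-up care, fixed X with period terms gives 0.53–0.74 at 6 months and 0.42–0.62 at 12 (3- to 6-month steps). Survey-date coding without period terms gives 0.62–0.86 and 0.66–0.80. Adding an indicator for controls whose PCP has since been trained returns the fixed-X estimates to about 1.00, if the spill-over is constant.

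**The case against.** **The coding may be the intended one.** The requirement for a PCP-and-time-point indicator sits close to a remark that each time point surveys different patients, which suggests rollout periods rather than repeat surveys. The one worked case has X constant within an adolescent. The sentence on within-adolescent information is weak evidence, because X·T_k uses within-person change even when X is constant. This stands: a reader might infer that the plan definitely recodes controls as treated, and the text does not establish that. It leaves the rule unstated. The subscript, the provider-level definition and the varying number of post-intervention assessments favour survey-date coding without proving it.

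**k may be calendar time.** Section 3.3.2 also indexes the outcome by time interval and says the beta_k capture temporal trend; Section 3.3.3 merges the two ideas. The ambiguity is real but does not rescue the model. If k is a calendar interval, X_ijk is most naturally the provider's status in that interval, and the recoding follows.

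**Dilution is not assured.** A reader might infer that survey-date coding always biases towards no effect. Step 2 shows that an upward trend with low correlation can reverse the sign, and Section 3.3.2 itself expects within-patient correlation not to be strong.

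**Fixed X is not always closer.** Trained PCPs also receive feedback on follow-up care, so spill-over is plausible, and at 50% survey-date coding is nearer 1 for that outcome. The choice of X is partly a choice of estimand, which the plan should state.

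**There is still time.** An analysis plan is to be presented before each analysis. That is the right place for the repair, but not a reason to leave the definition open.

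**Conclusion.** The concern holds as a gap with consequences under either reading: exposure at follow-up is undefined for adolescents enrolled before crossover, and both codings mislead in the equation as written. Survey-date coding misclassifies 32–71% of control follow-up surveys and can make the 12-month effect inestimable. With no trend it makes alpha falsely negative and dilutes alpha+gamma_k; with a trend the direction is not known in advance. Index-visit coding without calendar terms carries a linear trend into alpha and alpha+gamma_k, but not into gamma_k.

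Reading gamma_k alone gives only partial relief under survey-date coding. It is nearly unbiased at correlation 0.5 but not at 0.1, and it offers no change from baseline for follow-up care.

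Every size rests on the assumed step length, even enrolment, variance components, trend and persistent effect. The timeline figure is not shown, and the linear projection is only illustrative for binary outcomes. Confidence in the favoured reading is medium; the need for a stated rule does not depend on it.

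**What to change.** Make these changes together, before the analysis plan is presented:

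1. Define X once per adolescent from PCP/clinic implementation status at the index appointment, constant over T1–T5. State the estimand: the effect of an index visit under the intervention versus usual care.
2. Add enrolment-period fixed effects, separate from the assessment indicators T_k.
3. Read the follow-up effect from gamma_k, or from alpha+gamma_k with the calendar terms in the model. Do not read alpha alone as the treatment effect where T1 is the reference. For follow-up care, with T3 as reference, read alpha (3 months) and alpha+gamma_k (6 and 12 months) with the calendar terms.
4. Pre-specify alongside the main model, for follow-up care too, an analysis with a separate time-varying indicator for controls whose PCP has been trained since the index visit.
5. As a further sensitivity analysis, replace enrolment period by calendar period at the survey date. Enrolment-period terms do not remove a non-linear trend from gamma_k: an assumed jump of 0.5 at month 12 gives 0.90–1.14 at 3 and 6 months and 0.71–0.86 at 12, against 1.00 with survey-date terms.

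**Cost.** A defining sentence, the derived indicators and no new data. Under the same assumptions, enrolment-period terms leave the standard error of gamma_k unchanged and raise that of alpha+gamma_k by 17–28%. Survey-date terms raise them by 5–30% and 18–36% respectively (6 and 12 months). The extra control indicator adds 7–35% for gamma_k at 12 months. Under spill-over the main estimate is conservative: at 25%, gamma_k is 0.82–0.96 at 3 and 6 months and 0.75–0.87 at 12; at 50%, 0.64–0.92 and 0.50–0.74. That is why item 4 belongs beside the main model.
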